3.2.3 Tertiary endpoints

Tertiary endpoints will be measured continuously during ventilation period from day 8 up to day 28 after enrolment.

Efficacy

Efficacy of the investigational device will assess the ability to keep ventilation and oxygenation variables in optimal target ranges.

This endpoint will be determined by the percentage of time spent with six (6) variables in the optimal range during day 8 through day 28:

- 1) Tidal volume (VT)
- 2) Maximum pressure (Pmax)
- 3) Oxygen saturation measured by pulse oximetry (SpO₂)
- 4) End-tidal partial pressure of carbon dioxide (PetCO₂)
- 5) Respiratory rate (RR) for spontaneous breathing subjects
- 6) Pmax-PEEP for passive ARDS subjects

The optimal and sub-optimal ranges are defined by pertinent guidelines for different clinical conditions including normal lungs, brain injury, ARDS, and chronic hypercapnia.

Tertiary endpoints will be measured continuously during ventilation period from day 8 up to day 28 after enrolment.

Safety:

The tertiary safety endpoint will be determined by percentage of time spent with at least one variable in the sub-optimal range from day 8 up to day 28 after enrolment.

3.3 Study Design

EASIVENT is a Pivotal, two-arm, controlled, single-blind, multicenter, randomized trial of INTELLiVENT-ASV versus non automated Ventilation in adult ICU subjects.

3.3.1 Randomization

The subjects will be randomized to either INTELLiVENT-ASV or Non-automated Ventilation using in a 1:1 ratio by a computerized central randomization system.

The two study arms will be stratified by subject condition at inclusion (normal lungs, ARDS, chronic hypercapnia, or brain injury) and by site to ensure balanced assignment for interventions at each site. The randomization scheme will be generated and maintained by the randomization module part of the electronic case report form (eCRF).

3.3.2 Blinding

Study subjects will be blinded to the random intervention assignment of all study participants. Therefore, this study is considered single blind since study staff will know each subject's intervention assignment.

3.3.3 Justification for the design of the clinical investigation

The reference treatment used for comparison is a combination of controlled modes for passive subjects (volume control or pressure control) and assisted/spontaneous modes for active subjects (synchronized intermittent mechanical ventilation or pressure support).

Sample size has been adjusted with an adaptive design to be able to fulfill the targeted endpoints (see section 3.4).

3.4 Sample Size Determination

A minimum of 254 and maximum of 508 subjects will be included in this study, based on adaptive sample size assessments at scheduled 2nd interim analysis. Subjects will be selected for this study according to Section 7 (Study population) of the protocol.

Requirements related to participant withdrawal from the study are described in Section 7.6 (Study Withdrawal) of the protocol. All sites will have a minimum number of enrolment targets in order to meet overall cross-site enrolment and protocol goals.

Inclusion will be halted at sites that reach the 15% inclusion cap of total enrolment and a 50%-50% geographic distribution (EU vs US) in terms of patients is expected.

3.4.1 Group sequential design with 2 interim analyses

The planned sample size is a minimum of 254 and a maximum of 508 subjects.

The sample sizes for this trial are calculated using the following assumptions:

- significance level equal to 0.025 (1-sided)
- power of 0.8 (at final analysis)
- allocation ratio of 1:1
- Two interim analyses at half and three-quarter information time (i.e. when half and three-quarter of the subjects are evaluable for response), using spending functions with O'Brien-Fleming-Type boundaries for efficacy and futility.
- Efficacy endpoint (%All in optimal, more is better) on logit-scale:
 - Mean conventional = -1.86
 - Mean INTELLiVENT-ASV = -1.28
 - \circ Sd = 1.5 for both devices
- Safety endpoint (%Any in sub-optimal, less is better) on logit-scale:
 - Mean conventional = -0.09
 - Mean INTELLiVENT-ASV = -0.74
 - \circ Sd = 1.6 for both devices
- Correlation between endpoints = -0.85
- Dropout could occur when subjects are ventilated for less than 24 hours after inclusion because of unexpected death, transfer to another ICU or withdrawal of informed consent. A maximum dropout rate of 5% of these cases is expected. Given the large uncertainty on the assumed performance differences and the inclusion of a sample size reassessment, the initial sample size is not increased to deal with this dropout rate. At the second interim the sample size will be re-estimated, taking this observed dropout rate into account.

The table below shows the sample sizes and characteristics of a study with 2 interim analyses, with O'Brien-Flemming boundaries for efficacy and futility. The final sample size for this group sequential design is 254. 254 stands for the number of subjects with evaluable endpoints and means more subjects might have to be enrolled to reach this number. The p-values for significance are increasing at each analysis while the p-value to stop for futility decreases from the first interim analysis to the final analysis. The study has a high probability to stop at the first interim analysis if both ventilation modes have an equal performance.

Sample sizes and operational characteristics for the trial using O'Brien Fleming boundaries for futility and efficacy.

Analysis	SS	Z	Nominal p	α Spend	end Power	
		Efficacy	Efficacy		(Prob stop H _A)	
1 (IA1)	128	2.96	0.0015	0.0015	0.25	

2 (IA2)	192	2.36	0.0093	0.0097	0.
3 (final)	254	2.02	0.0220	0.0250	0
Analysis	SS	Z	Nominal p	Prob Futility Stop	
		Futility	Futility	(Prob stop under H ₀)	
1 (IA1)	128	0.44	0.3315	0.67	
2 (IA2)	192	1.34	0.0904	0.25	
3 (final)	254	2.02	0.0220	0.06	

Recorded data has to be 24 hours at minimum, and 80% of the invasive ventilation duration have to be recorded in the Memory box. Note that subjects for which less than 80% of mechanical ventilation time could be recorded due to documented technical reasons, the recorded data (with 'percent spent' calculated per the recorded time) will be used for the primary analysis of the co-primary endpoints.

3.4.2 Adaptive sample size increase

An adaptive sample size reassessment is foreseen at the second interim analysis. In case promising results are obtained at this interim analysis, additional resources will be committed to the trial. Following Mehta and Pocock (Mehta, 2011), sample sizes will only be increased in case the interim results are promising, in which case the overall type-I error is not inflated by use of the conventional Wald Statistic. The maximum number of additional subjects will be capped at 254 (above the pre-planned 254 subjects) or a maximal total sample size of 508. More specifically, this 'promising zone' is defined in terms of the conditional probability of rejecting the null hypothesis at final analysis, given the estimated performance difference at interim ('conditional power') and assuming that this estimated performance difference is the true underlying difference. Depending on the conditional power (CP) for each of the two endpoints at the second interim analysis, three different zones and anticipated actions are to be considered:

1) **Unfavourable zone**: At least one endpoint with CP < 0.33.

The interim results are so disappointing that it is not worth to increase the sample size to retrieve CP and the original sample size is retained. This zone is defined as 0 to 0.33, for a sample size reassessment at 0.75 information fraction. If the CP for either of endpoints is below 0.33, this is considered unfavourable, and no sample size increase will be performed.

Promising zone: Both endpoints with CP >0.33, at least one endpoint with CP <0.80

If the CP is above 0.33 but below the originally planned 0.80 for at least one primary endpoint, the sample size will be increased by just the right amount to recover the targeted power of 0.80, while not exceeding the pre-specified maximal sample size of 508 subjects. As stated above, both endpoints would need to have a CP above 0.33 and one endpoint a CP below 0.80 to embark on a sample size increase. The sample size increase will be set to the highest of two recalculated sample sizes if both endpoints have a CP between 0.33 and 0.80.

3) Favourable zone: Both endpoints CP >0.80

The conditional power at second interim analysis is 0.80 or larger for both endpoints. In this zone, the interim results are sufficiently favourable that the trial continues to the original sample size without the need to adaptively increase the trial size.

4. General Analysis Definitions

Data will be expressed by mean±SD or median (interquartile range) depending on the normality of the distribution assessed with Kolmogorov-Smirnov test. Comparisons will use the two sample Z-test on log-transformed primary endpoint variables. P values <0.025 (one-sided) will be considered significant. Bonferroni adjustment will be applied when applicable. Data will be analyzed using SAS (Version 9.4 or higher).

The tables will be created by treatment arm. Listings with individual values will be provided for all data presented in the tables.

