10.2 Sample Size Determination

A minimum of 254 and maximum of 508 subjects will be included in this study, based on adaptive sample size assessments at scheduled interim analyses. Subjects will be selected for this study according to Section 7 of this protocol. Requirements related to participant withdrawal from the study are described in Section 7.6. All sites will have a minimum number of enrollment targets in order to meet overall cross-site enrollment and protocol goals.

Inclusion will be halted at sites that reach the 30% inclusion cap of total enrollment.

Sample sizes for a group sequential design with 2 interim analyses

The planned sample size is a minimum of 254 and a maximum of 508 subjects.

The sample sizes for this trial are calculated using the following assumptions:

- significance level equal to 0.025 (1-sided)
- power of 0.8 (at final analysis)
- allocation ratio of 1:1
- Two interim analyses at half and three-quarter information time (i.e. when half and three-quarter of the subjects are evaluable for response), spending functions with O'Brien-Fleming-Type boundaries for efficacy and futility. Efficacy endpoint (%All in optimal, more is better) on logit-scale:
 - Mean conventional = -1.86
 - Mean INTELLiVENT-ASV = -1.28
 - $S_d = 1.5$ for both devices
- Safety endpoint (%Any in sub-optimal, less is better) on logit-scale:
 - Mean conventional = -0.09
 - Mean INTELLiVENT-ASV = -0.74
 - $S_d = 1.6$ for both devices

- Correlation between endpoints = -0.85
- Dropout could occur when subjects are ventilated for less than 24 hours after inclusion because of unexpected death, transfer to another ICU or withdrawal of informed consent. A maximum dropout rate of 5% of these cases is expected. Given that the large uncertainty on the assumed performance differences and the inclusion of a sample size reassessment, the initial sample size is not increased to deal with this dropout rate. At the second interim the sample size will be re-estimated, taking this observed dropout rate into account.

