4.3.1 Intention-To-Treat (ITT) Population

The Intention-To-Treat population (ITT) will consist of all randomized subjects. Subjects who receive the wrong ventilation support will be analysed in the arm to which they were randomized. The ITT population will be used for primary, secondary, and tertiary efficacy analyses.

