4.9 Changes to Protocol

The protocol indicates that inclusion will be halted at sites that reach the 30% inclusion cap of total enrolment. This cap was changed to 15% in this SAP following request from the FDA.

5. Study Subjects

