7.1 Primary Efficacy Variable

The primary efficacy endpoint is a composite endpoint to assess the ability to keep the ventilation and oxygenation variables in optimal target ranges. The primary efficacy variable will be calculated as the percentage of time spent with **ALL** six variables in the optimal target ranges during the **7 days** after randomization:

- 1) Tidal volume (VT)
- 2) Maximum pressure (Pmax)
- 3) Oxygen saturation measured by pulse oximetry (SpO₂)
- 4) End-tidal partial pressure of carbon dioxide (PetCO₂)
- 5) Respiratory rate (RR) for spontaneous breathing subjects
- 6) Pmax-PEEP for passive ARDS subjects

The optimal and sub-optimal ranges are defined by pertinent guidelines for different clinical conditions including normal lungs, brain injury, ARDS, and chronic hypercapnia.

The primary efficacy variable will be expressed by median (interquartile range). Log transformation will be performed on the data before performing the 2 sample Z-test. Comparisons will use the 2 sample Z-test for log transformed variables. The P values <0.025 (one-sided, the hypothesis is that INTELLiVENT-ASV is better than "non-automated ventilation" on the Hamilton Medical Ventilators, in terms of efficacy) will be considered significant.

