8.2 Primary Safety Variable

The primary safety variable will be calculated as the percentage of time spent with **at least one** of the six variables in the sub-optimal target ranges during the **7 days** after randomization:

- 1) Tidal volume (VT)
- 2) Maximum pressure (Pmax)
- 3) Oxygen saturation measured by pulse oximetry (SpO₂)
- 4) End-tidal partial pressure of carbon dioxide (PetCO₂)
- 5) Respiratory rate (RR) for spontaneous breathing subjects
- 6) Pmax-PEEP for passive ARDS subjects

The primary safety variable will be expressed by median (interquartile range). Log transformation will be performed on the data before performing the 2 sample Z-test. Comparisons will use the 2 sample Z-test for log transformed variables. The P values <0.025 (one-sided, the hypothesis is that INTELLiVENT-ASV is better than conventional non-automated ventilation in terms of efficacy) will be considered significant.

Primary safety variable will be performed on the safety population.

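### Both co-primary endpoints are sized on the logit scale but tested on the log scale; as written, joint power at 254 subjects is about 0.75, not 0.80

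*SAP*

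**What the plan says.** **Sizing.** Protocol 10.2 and SAP 3.4.1 give identical design assumptions on the logit scale: "Efficacy endpoint (%All in optimal, more is better) on logit-scale" and "Safety endpoint (%Any in sub-optimal, less is better) on logit-scale". From these, with one-sided alpha 0.025 and two interim looks, they arrive at 254 evaluable subjects and power 0.8.

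**Analysis.** SAP 4 sets the general rule: "Comparisons will use the two sample Z-test on log-transformed primary endpoint variables". SAP 7.1 applies it to efficacy ("Comparisons will use the 2 sample Z-test for log transformed variables") and SAP 8.2 to safety ("Log transformation will be performed on the data before performing the 2 sample Z-test"). SAP 7.3 and 8.4 use the same wording for the tertiary endpoints. No analysis section mentions a logit. Protocol 10.4.5 names no test or transformation, so the SAP alone defines the primary test.

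**Reconciliation.** SAP 4.9 records one departure from the protocol, the site enrolment cap: "This cap was changed to 15% in this SAP following request from the FDA". It does not mention the scale.

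**Boundary values.** SAP 4.3.1 says "The ITT population will be used for primary, secondary, and tertiary efficacy analyses", and SAP 8.2 puts the primary safety analysis on the safety population. SAP 4.8 deals with missing recordings. Neither document says how to transform an observed 0% or 100%.

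**The concern.** Log and logit nearly coincide when the percentage is small and separate as it grows. The assumed efficacy means of -1.86 and -1.28 correspond to about 13% and 22% of time, where the choice matters little. The assumed safety means of -0.09 and -0.74 correspond to about 48% and 32%, where it matters more. A programmer following the SAP would code the log, and the trial would then test a smaller standardised safety effect, with a weaker correlation between the endpoints, than the design assumed. Both changes lower the chance that the two endpoints succeed together. The interim Z values and the conditional power that decides on a sample size increase also depend on the scale.

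The boundary gap exists on either scale. A subject with no time fully in the optimal range, or none with a variable in the sub-optimal range, has no defined value. An observed zero could then be treated as missing, or be offset by a constant chosen later, and the choice changes the result.

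**Working it through.** **Inputs (Protocol 10.2, Table 5; SAP 3.4.1).** Logit means are -1.86 vs -1.28 for efficacy (SD 1.5) and -0.09 vs -0.74 for safety (SD 1.6), with correlation -0.85. Looks are at 128, 192 and 254 subjects (64, 96 and 127 per arm). Efficacy bounds are Z = 2.96, 2.36, 2.02; interim futility bounds are Z = 0.44, 1.34.

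**Assumptions not in the documents.** Both endpoints must succeed, futility on either stops the trial, and the percentages are logit-normal within each arm with the stated parameters.

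**Step 1: reproduce the plan on the logit scale.**

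- Standardised effects: efficacy 0.58/1.5 = 0.387; safety 0.65/1.6 = 0.406.
- Expected final Z = effect × √(127/2): 0.387 × 7.97 = 3.08 and 0.406 × 7.97 = 3.24.
- Through the three looks: efficacy alone 0.836, safety alone 0.870, joint 0.799 by patient-level simulation (60,000 trials, Monte Carlo SE 0.002). A separate calculation on the joint distribution of the Z statistics gives 0.800. The stated 0.80 is reproduced.
- The power column of Table 5 sums to 0.25 + 0.43 + 0.19 = 0.87. It matches the safety endpoint alone (0.254 + 0.424 + 0.193 = 0.871), so those stage figures are for a single endpoint.

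**Step 2: same subjects, test on log p.** With x the logit, log p = -log(1 + e^(-x)).

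| | Difference | Average SD | Standardised effect | Expected final Z |
|---|---|---|---|---|
| Efficacy | 0.437 | 1.155 | 0.379 | 3.02 |
| Safety | 0.371 | 0.966 | 0.384 | 3.06 |

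The correlation between endpoints weakens from -0.85 to about -0.74. Efficacy alone falls to 0.822 and safety alone to 0.833. Joint power is 0.754 (0.751 by the separate calculation).

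**Step 3: vary the assumptions.** N = 254 except in the last row.

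| Joint power | Logit | Log |
|---|---|---|
| Futility on either endpoint | 0.799 | 0.754 |
| Futility only if both fail | 0.823 | 0.782 |
| No futility stop | 0.830 | 0.787 |
| Correlation -0.65 | 0.773 | 0.730 |
| Correlation -0.95 | 0.825 | 0.766 |
| With second-interim increase, cap 508 | 0.831 | 0.790 |

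The loss is 4 to 6 points throughout. Without the increase, the log test reaches 0.80 at about 282 to 284 subjects (0.799 at 282, 0.802 at 284), which is 28 to 30 more: 28/254 = 11%, 30/254 = 12%.

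**Step 4: boundary rule.** Take log((p + c)/(1 - p + c)) as an example. At p = 0 it equals log(c/(1 + c)). The documents give no frequency of zeros, so suppose 2% of each arm were at 0% on efficacy:

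| c | Value at 0% | Joint logit power |
|---|---|---|
| 0.01 | -4.62 | 0.75 |
| 0.005 | -5.30 | 0.74 |
| 0.001 | -6.91 | 0.70 |
| 0.0001 | -9.21 | 0.63 |

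With c = 0.0001 each zero lies (9.21 - 1.86)/1.5 = 4.9 SDs below the control mean, which inflates the variance. With no zeros, the first three constants leave joint power at 0.798 to 0.800.

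**The case against.** **Log may be loose wording for logit.** This is plausible, since every sizing input is on the logit scale. If so, the power figure is untouched and only the text is wrong. But the wording recurs in five SAP sections and would be programmed as written.

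**The planned adaptation recovers most of the loss.** With the increase at the second interim, log-scale power is 0.790, one point below 0.80. That is a fair point about the whole design. The plan's 0.80, however, is its figure for 254 subjects, and on equal terms the gap remains about 4 points (0.831 vs 0.790).

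**The omission from SAP 4.9 proves little.** The protocol names no primary test, so a log test is not plainly a protocol change. This stands: the conflict is between the logit-scale sizing and SAP 4, 7.1 and 8.2.

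**The boundary rule would not be chosen by unblinded staff.** Protocol 1.4 gives the analysis to an independent blinded statistician. That weakens the concern about a choice influenced by knowledge of allocation, although bedside staff do know the arm. It does not supply the missing rule.

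**The cost of zeros is hypothetical.** It is. The 2% is an assumption, and under it even c = 0.005 gives 0.74. The figures show that the choice of constant can matter, not how much it will.

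Nothing here shows that the type I error is affected.

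**Conclusion.** The concern holds. The sizing and the primary test are on different scales, and no text reconciles them. If log is meant literally, joint power at 254 before any increase is about 0.75 instead of 0.80. The loss is 4 to 6 points under every variant tried, and power is 0.79 instead of 0.83 once the planned increase is included. This rests on logit-normal percentages with the stated parameters and on joint success; the 0.80 starting point also needs futility on either endpoint to stop the trial. If log is a slip, there is no power loss and the defect is one of wording. The missing rule for 0% and 100% is a separate gap whose numerical effect cannot be known from the documents. This should be fixed; it does not invalidate the design.

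**What to change.** 1. Replace log with logit in SAP 4, 7.1 and 8.2, and in 7.3 and 8.4 for consistency.
2. State that the interim Z values, the conditional power and the final test all use that scale.
3. If log is really intended, say so and restate joint power at 254 as about 0.75.
4. Before any unblinded look, fix one rule for 0% and 100% that keeps every subject in the relevant analysis population and is the same in both arms and for both endpoints. One example is log((p + c)/(1 - p + c)) with c = 0.005 (0.005 × 7 × 24 × 60 = about 50 minutes of seven full days), with sensitivity analyses at c = 0.01 and 0.001. Any sensible pre-specified rule would close the gap.

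The cost is wording in up to five SAP sections, minor programming and one added sensitivity analysis. No extra patients are needed if logit is used.

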4.1 Study Period and Participant Duration

4.1.1 Study Periods

Screening period: Starting the day of signature of informed consent up to and including the day before randomization. For subjects who are not randomized, the screening period will end on the day the subject is determined to be a screen failure.

Randomization (Day 0): After screening assessments are completed and subject's eligibility confirmed, the subject will be randomly assigned (1:1) to the automated ventilation with INTELLiVENT-ASV or to the non-automated ventilation. Randomization will be stratified according to the clinical condition at inclusion (normal lungs, ARDS, chronic hypercapnia, brain injury).

Intervention period (Day 1 – Day 27): From inclusion up to day of extubation (and not re-intubated within 48h after extubation), even if subjects remain on mechanical ventilation. During this period, subjects re-intubated within 48h after extubation will be kept in the study. Subject re-intubated beyond 48h will be considered as weaned from the ventilation.

The INTELLiVENT-ASV or control arm ventilator protocols will be continued until subjects are able to breathe unassisted for 48 hours, death, ICU discharge, study withdrawal, or day 28, whichever comes first.

Dropout could occur when patients are ventilated for less than 24 hours after inclusion because of unexpected death, transfer to another ICU, or withdrawal of informed consent. We expect a maximum of 5% of these cases.

Note a maximum of 5% of subjects are anticipated for which not 80% of mechanical ventilation time within the allocated randomized ventilation mode could be recorded due to documented technical reason. The recorded data will be used (with 'percent spent' calculated per the recorded time) for the primary analysis of the co-primary endpoints. As a sensitivity analysis, these values will be treated as missing data.

End of Study and participation duration (Day 1- Day 28):

Each enrolled subject will be followed for a maximum of 28 days. Prior to completion of study close out, all subject data must be captured and monitored in the eCRF.

The end of study visit should be completed at the time a subject completes the study. A subject will be considered to have completed the study for the following reasons:

- Subject completes follow-up visits as until day 28 as per investigational plan.
- Subject dies.
- Subject or legally authorized representative requests to be withdrawn from the study.
- Investigator requests to be withdrawn from the study to protect the welfare of the subject.

Subject re-intubated within 48h after extubation will continue to be followed up until day 28. Subject re-intubated beyond 48h will be considered as weaned for the ventilation procedure. They remain in the study but only a phone call will be done at Day 28.

See Appendix 1 in the SAP for a detailed schedule of assessments.

There is no replacement of subjects. Dropout could occur when patients have less than 80% of the invasive ventilation duration recorded or when patients are ventilated for less than 24 hours after inclusion because of unexpected death, transfer to another ICU, or withdrawal of informed consent.

